#### 14.3.2.6. Maximum Tolerated Dose

For Phase 1a, a table will be presented showing the MTD as well as a summary of the dose escalation and any subsequent dose reductions.

#### 14.3.3 Other Analyses

### 14.3.3.1. Antineoplastic Activity

#### Phase 1a

As the primary objective in the Phase 1a portion of the study is to determine the MTD and to evaluate the safety of the study treatment, all antineoplastic activity analyses will be descriptive and exploratory in nature. Disease status will be summarized by cycle and dose group,

# **FORBIUS**

including changes from baseline. As a secondary objective, OR, duration of OR, SD, and TTP will be assessed and calculated, wherever possible, according to standard response criteria (see **Appendix F**; Measurement of Effect).

#### Phase 2a

As a primary objective of the Phase 2 portion of the trial, OR, duration of OR and SD, as well as TTP will be assessed and calculated, wherever possible, according to standard response criteria (see **Appendix F**; Measurement of Effect). Frequency counts and percentages will be presented for an objective response rate (ORR) and disease control rate (DCR). For analysis of TTP, the median time to event and 95% confidence intervals will be calculated using the Kaplan-Meier method.

#### **Response Calculations**

In the event of an OR (CR or PR) the duration of the OR will be determined from the day the initial response is observed (using screening/baseline images for comparison) to the day that progression is observed. Duration of SD (minimum duration of not less than 8 weeks) will also be assessed using the time from the first dose of AVID100 to the day that PD is documented.

The ORR will be calculated as the proportion of patients who achieve either a complete response or a partial response (CR+PR). ORR, time to OR, and duration of OR will be determined.

DCR will be calculated as the proportion of patients who achieve either a complete response, partial response, or disease stabilization for a minimum of 8 weeks (CR+PR+SD).

TTP will be measured from the treatment start date (date of first dose) to either the date the patient is first recorded as having disease progression (even if the patient went off treatment because of toxicities), or the date of death if the patient dies due to any cause before progression. If a patient is lost to follow-up, the patient will be censored as of the date of last contact. Patients who start a new treatment before they progress will be censored as of the date of start of the new treatment. If a patient has not progressed nor died, time to progression is censored at the date of last follow-up. TTP will be analyzed using the method of Kaplan and Meier.

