# 7.4.3 Diagnostic Imaging for Assessment of Disease (and Pulmonary Status)

(To include diagnostic imaging by computerized tomography [CT] or magnetic resonance imaging [MRI] of the chest with each evaluation (for disease evaluation where indicated, and to assess for evidence of pulmonary fibrosis) plus abdomen and pelvis, and other sites as indicated based on tumor type and clinical judgment in order to assess the status of the underlying malignancy. Use of contrast is preferred but is at the discretion of the Investigator, as medically indicated.

The same method(s) of disease evaluation and the same technique should be used throughout the study. The location and dimensions of "marker" lesions, where such information is available, will be documented on the patient's eCRF. Standard response criteria will be applied for disease assessments and response evaluations [see **Appendix F**; Measurement of Effect]).

- Screening
- End of Cycle 2 (and every even-numbered cycle thereafter)\*
- At least 4 weeks following documentation of an OR
- EOT (if > 6 weeks since previous assessment)
- 1M FUP (if PD was not documented before or at EOT)
- Extended Follow-up\*\* (in the event of an ongoing OR or SD at EOT)
  - o Every 3 months during the first year of follow-up
  - o Every 6 months thereafter

If PD is documented at any time no further disease assessments will be required. Patients with documented PD will be discontinued from further treatment with study drug so that alternative management of their malignancy may be considered.

To be assigned a status of partial response (PR) or complete response (CR), changes in disease status must be confirmed by repeat studies performed 4 weeks (+ 7 days) after the criteria for response are first met. In the case of SD, follow-up measurements must have met the SD criteria at least once after study entry at for a minimum duration in general not less than 8 weeks.

\*End of Cycle assessments may be conducted at any time during the week prior to Day 1 of the next cycle.

\*\*To continue at the intervals specified until disease progression or another therapeutic intervention is initiated; documentation may be submitted in writing, an in-person visit will not be required.

In the event of an ongoing OR or SD at the EOT, data will continue to be collected on the duration of OR or SD, as well as on the overall time to PD.

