## F. PROGRESSION-FREE SURVIVAL

PFS is defined as the duration of time from start of treatment to time of progression or death, whichever occurs first.

Adapted from: Eisenhauer EA, Therasse P, Bogaerts J, et. al. New response evaluation criteria in solid tumours: revised RECIST guideline (version 1.1). Eur. J. Cancer. 2009; 45:229-247.

<http://www.eortc.be/recist/documents/RECISTGuidelines.pdf >

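### Time to progression is defined as progression-free survival, and its censoring dates are not tied to the last tumour assessment

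*Combined protocol and SAP*

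**What the plan says.** Section 14.3.3.1, Phase 2a, introduces the endpoint: "As a primary objective of the Phase 2 portion of the trial, OR, duration of OR and SD, as well as TTP" are to be assessed by the criteria in Appendix F. The summary is fixed there too: "For analysis of TTP, the median time to event and 95% confidence intervals will be calculated using the Kaplan-Meier method".

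The Response Calculations text then gives the rules.

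- **Events:** progression, "or the date of death if the patient dies due to any cause before progression". The clock starts at first dose.
- **Censoring, lost patients:** "If a patient is lost to follow-up, the patient will be censored as of the date of last contact".
- **Censoring, new therapy:** "Patients who start a new treatment before they progress will be censored as of the date of start of the new treatment".
- **Censoring, everyone else:** "If a patient has not progressed nor died, time to progression is censored at the date of last follow-up".

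Appendix F, part F, reads: "PFS is defined as the duration of time from start of treatment to time of progression or death, whichever occurs first". Appendix F does not define TTP.

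Section 7.4.3 places on-treatment imaging at "End of Cycle 2 (and every even-numbered cycle thereafter", which with 21-day cycles is every 6 weeks. After end of treatment (EOT), imaging every 3 months and later every 6 months applies only if a response or stable disease is ongoing.

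**The concern.** There are two separate problems, and they push in different directions.

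The first is the name. A TTP that counts death from any cause is PFS. A reader who sets the reported median beside a TTP from another study would compare different quantities.

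The second is the censoring date. Progression here is established by tumour assessment, so a patient is known to be progression-free only up to the last evaluable one. None of the three censoring dates refers to an assessment. A patient who stops being scanned but is still contacted stays in the risk set without being able to show progression on a scan, while a death in that time would still count.

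What is at stake is the reported Phase 2a median, its interval and the curve, in cohorts of about 15 patients (Section 14.2) that will not be topped up by replacement (Section 9.2). No hypothesis test depends on them.

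**Working it through.** **Is there a figure to reproduce?** No. The documents give no TTP or PFS median, event count or loss rate.

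**Definitions side by side.** TTP in Section 14.3.3.1: origin at first dose; events are progression or death from any cause. PFS in Appendix F: origin at start of treatment; events are progression or death. They are the same endpoint.

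**Can contact outlast scanning?** Yes, by three routes.

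- Drug-related toxicity unresolved at the 1-month visit is followed at about 3 and possibly 6 months after the last dose, by telephone or in writing (Sections 6.11 and 7.2.2).
- Scheduled scans may be missed.
- New therapy may start between extended-follow-up scans, which are 3 or 6 months apart.

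**Direction of the censoring effect.** The Kaplan-Meier estimate is S(t) = product over event times of (1 - d/n), with d events among n at risk. A later censoring date leaves every d unchanged and can only keep or increase n. Each factor, and so S(t), stays the same or rises.

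**Worked example (hypothetical, n = 15).** Progressions: 4, 3, 2 and 1 at 1.4, 2.8, 4.1 and 5.5 months. Two patients are progression-free at 12 months. Three were last scanned at 1.4 months and last contacted at 6 months.

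| Month | Events | At risk, last contact | S(t) | At risk, last scan | S(t) |
|---|---|---|---|---|---|
| 1.4 | 4 | 15 | 0.733 | 15 | 0.733 |
| 2.8 | 3 | 11 | 0.533 | 8 | 0.458 |
| 4.1 | 2 | 8 | 0.400 | 5 | 0.275 |
| 5.5 | 1 | 6 | 0.333 | 3 | 0.183 |

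The median is 4.1 months under last contact and 2.8 months under last scan.

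**Simulation.** Only the 6-week scan interval comes from the documents. Assumed: median time to progression 2.5 or 4 months; median time to death 12 months; 10, 20 or 30% stop being scanned by 6 months; contact lasts 0-0.1, 0-1.4, 1-3 or 3-6 months beyond scanning; 12-month cutoff. This makes 2 x 3 x 4 = 24 scenarios of 20,000 patients. Results are for the 6-month estimate, in percentage points.

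- **Protocol rule minus last-scan rule:** from 15.6 - 15.3 = 0.3 to 22.9 - 14.2 = 8.7.
- **Protocol rule minus complete-follow-up PFS:** -0.1 to +0.2 when contact ends with scanning; +0.9 to +3.5 with contact 1-3 months beyond; +2.0 to +7.3 with 3-6 months beyond.
- **Last-scan rule minus complete-follow-up PFS:** -0.2 to -2.3.
- **Protocol rule minus TTP with deaths censored (last-scan censoring):** about 2 to 11 points lower in 23 scenarios, and level (22.9 - 22.7 = +0.2) in the other.

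**Small samples.** With median progression 3 months, 20% loss and contact 0-6 months beyond scanning, 3,000 replicates at n = 15 gave a mean 6-month difference between the rules of 4.2 points (95th percentile 12.5). The median was longer under the protocol rule in 47% of replicates and not longer in 53%. A second check used fixed 6-weekly scans, true medians of 9 or 13 weeks, 10-30% stopping scans, and contact 4.3, 6 or 13 weeks past the last scan. The large-sample median was identical under both rules in all 18 scenarios, and at n = 15 it was unchanged in 64-100% of replicates.

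**The case against.** The strongest reply is that the schedule leaves little unscanned time. Section 7.4.3 asks for imaging at EOT if more than 6 weeks have passed, at the 1-month visit if progression is undocumented, and every 3 months while a response or stable disease continues. Section 7 puts EOT evaluations before any new treatment, so a patient moving straight from study drug to other therapy has a gap of about one scan interval. There is no separate survival follow-up. This stands as a limit on size: where contact ends with scanning, the bias is about zero. It does not reach the three routes above.

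A reader might also take the provision for written documentation in extended follow-up (Sections 6.11 and 7.4.3) to mean that contact replaces scans. It does not. What may be submitted in writing is the imaging-based response assessment. The telephone or written contact that matters is the adverse-event follow-up, and that applies only when drug-related events persist.

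Importance is also limited. The Phase 2a primary objective in Section 3.2.1 does not name TTP, Section 14.1 rules out inferential tests, and the expansion decisions in Section 14.2 rest on response rate, with durability of response and stabilization also considered. At n = 15 the approximate 95% half-width around 0.28 is 1.96 x sqrt(0.28 x 0.72 / 15) = 0.23, wider than any shift in the scenarios. All of this stands, and it makes the point modest.

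Finally, Section 14.3 promises a detailed SAP before database lock. The rule could be refined there, but Section 14.3.3.1 is the stated rule, and nothing else in the supplied text repairs it.

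**Conclusion.** The point holds in two parts. By the protocol's own Appendix F, the endpoint called TTP is PFS; this needs no assumption. The censoring dates ignore the last tumour assessment, so the curve is equal to or higher than under last-assessment censoring, never lower.

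A reader might infer that the reported curve is biased upward overall. The documents do not support that. The upward effect belongs to the censoring rule alone; counting deaths works the other way, and against a TTP with deaths censored the net result is usually downward. Nor is last-scan censoring exact: because later deaths still count, it ran 0.2 to 2.3 points low.

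The size rests on assumed loss rates and contact gaps: about 0.3 to 8.7 points between the two rules at 6 months, with the planned summary, the median, often unchanged. For a descriptive endpoint this is a correction worth making, but not a threat to the trial's decisions.

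**What to change.** In Section 14.3.3.1:

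1. Rename the endpoint PFS, matching Appendix F. Alternatively keep TTP and censor deaths without documented progression, which usually makes the curve more favourable.
2. Censor patients without an event, lost to follow-up or starting new therapy at the last evaluable tumour assessment before that date, or at Day 1 if there is none.
3. State how a progression or death first recorded after missed scans is handled. Such a rule needs an agreed interval, so the 6-week imaging schedule in Section 7.4.3 and the 8-week re-evaluation in Appendix F must be reconciled.

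The cost is wording only, here and in the promised SAP, with no new data collection. If the endpoint becomes PFS, the reported curve will be slightly less favourable.

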#### **Imaging Data**

Imaging data (imaging studies and derived assessments) will be stored by the sites and will be available upon request for potential review by the Sponsor or an independent radiology reviewer. If an independent radiology review is conducted, a charter will be prepared and finalized by the Sponsor (or designee) prior to initiating the radiology reviews.

### 14.3.3.2. Pharmacokinetic Parameters

The PK profile of total antibody (AVID100 plus MAB100), AVID100, and DM1 will be determined by noncompartmental analysis using standard PK software (e.g., Phoenix WinNonlin). Parameters to be determined will include time of maximum observed concentration (Tmax), maximum (peak) concentration (Cmax), minimum (trough) concentration (Cmin), and area under the concentration curve for the last measurable concentration (AUClast). When the terminal elimination phase can be identified, additional parameters such as elimination half-life (T½), clearance (Cl), and volume of distribution (Vd) will be determined.

Evaluations to delineate dose-response and PK parameter-response relationships will be undertaken.

#### 14.3.3.3. Biomarker Parameters

Biomarker assessments, to include collection of archival or recent biopsy tissue for assessment of EGFR-expression and other potential biomarkers, will be conducted in on an optional basis in consenting patients in Phase 1a, and in all patients in Phase 2a.

A summary of the changes in potential biomarker(s) will be presented.

Biomarker analyses will be performed according to standard methodologies and will examine relationships between the biomarker assessments and clinical toxicities observed during the study. These analyses will be described in the SAP.

### 14.4. Clinical Study Report

Following study completion a final integrated clinical/statistical study report will be prepared. Further studies may be planned depending on a review of the data

# APPENDIX A Study Assessments

			TABI	LE 7:	: STU	J DY A	ASSE	SSMEN	TS SCH	IEDULE	,				
			YCLE 1				CYCL			BSEOUEN		EOT < 10d	1M FUP*	Extended	As
STUDY ASSESSMENTS	Screen	D1	D2	D4 +/- 1d	D8	D1	D8	End of Cycle 2	D1	D8	End of Even Number Cycles d	after decision to dis-continue	30 d (+7) after last dose	Follow Up* if OR or SD at EOT	Clinically Indicated
CONSENT AND MEDICAL HISTORY															
Informed Consent  / Eligibility Assessment	X														
Past Medical History	X														
History of Primary Malignancy 	X														
SAFETY ASSESSMENTS (1) (screening asses	sments withi	n 14 days prior to	o first sti	ıdy dru	g dose										
Medication Survey 	X									0 days after					
AE Assessments 			t through	30 day	ys after l	ast dose	; throug	h 3 months	or 6 months	to 2 years)	follow-up if associa				 
ECOG PS Evaluation	Х	X a				X			X			х	X		X
Phase 1a: Vital Signs 	x	SOI; EOI; 2, 4h after EOI	х	х		х			x			x	х		х
Phase 2a: Vital Signs 	X	SOI, EOI				X			X			х	X		X
Physical Exam/to include weight and	X	x a				х			x			x	х		x
pulmonary assessment 															_ ^
Hematology Panel 	X	x a		X	X	X	X		X	X		X	X		X
Serum Chemistry Panel 	X	x a		X	X	X	X		X	X		X	X		X
Coagulation Panel 	X	X a		X	X	X	X		X	X		х	X		Х
Urinalysis 	X	x a		X	X	X	X		X	X		х	X		Х
ADA to AVID100 		X				X			X			х	X		xe
Pregnancy Testing  (w/in 2 days of I st dose)	X	X										х			Х
ECG (12-lead) 	x	SOI, EOI, 30 min after EOI										x			x
SAFETY ASSESSMENTS (2) (screening asses	sments withi	n 28days (+/- 2)	prior to	first sti	udy druį	g dose p	rovided	no antineo	plastic thera	py has been	delivered between a	ssessment and	first dose of s	tudy drug)	
Ophthalmology Exam 	X										End of C2 only	X			х
MUGA Scan or Echo 	X											X			X
Pulmonary function tests 	X											x			X
Chest radiography (PA and lateral)	X											x			X
DISEASE ASSESSMENTS (screening assessm	ents within 2	28 days (+2d) prie	or to first	t study	drug do	se)									
Phase 1a only: Document EGFR positivity 	optional														
Phase 2a only: Document EGFR positivity 	required														
Phase 1a only: Tumor Marker Measurement 	x							х			x	x b		q3m for 1y, q6m after c	
Imaging for Disease (and Pulmonary Status) 	х							х			х	x b		q3m for 1y, q6m after c q3m for 1y,	
Response Assessment 								X			x	x b		q5m for fy, q6m after c	
ADDITIONAL ASSESSMENTS															
Phase 1a: PK Sampling 		SOI; EOI; 2, 4h after EOI	24h after EOI	х	x	SOI EOI	х		SOI EOI			х	х		xe
Phase 2a: PK Sampling 		SOI EOI			х	SOI			SOI, EOI-C5 only	C5 only		х	х		xe
Phase 1a: Archival Tumor for EGFR confirmation and biomarker studies 		optional; subm enrollme			r study										
Phase 2a: Tumor for exploratory studies 	required														

Phase 2a: Blood for Exploratory Studies 		x									х		
TRIAL TREATMENT													
AVID100 Infusion (2-h)		X				X			X				
Phase 1a: Post-Infusion Monitoring		4h				X			X				
Phase 2a: Post-Infusion Monitoring		2h				X			X				

\*Given the Q3W dosing frequency, EOT and 1M FUP evaluations may be combined in those situations where scheduling coincides, provided a minimum of 30 days of post-dosing follow-up have been observed.

Abbreviations: SOI-start of infusion; EOI-end of infusion; EOT-end of treatment; 1M FUP-1 month follow-up

- a Need not be assessed prior to Cycle 1 if  $\leq$  7 days since screening;
- b Conduct only if > 6 weeks since the previous assessment;
- c To be conducted in the event of ongoing objective response (OR) or stable disease (SD) at the end of treatment; continue until progressive disease (PD) or another therapeutic intervention is initiated d End of Cycle assessments may be conducted at any time during the week prior to Day 1 of the next cycle.
- e Additional ADA and PK sampling to be performed in the event of an IRR, as close as possible to the onset of the event
- 1. Informed Consent: To be signed prior to enrollment and prior to performing any protocol-related procedure, unless such testing was performed previously as part of the routine clinical management of the patient.
- 2. History of Primary Malignancy: To include details of the primary malignancy, including: histological/cytological classification; stage of disease at diagnosis and at entry; prior surgical procedures for the malignancy; prior antineoplastic therapy, prior radiation therapy, as well as dates of treatments, numbers of cycles, and best response to each therapy.
- 3. Medication Survey: To include period within 14 days prior to first study drug dose and throughout study for a period of 30 days following last study drug dose.
- 4. AE Assessments: To detail symptoms that may be present prior to/at the time of first administration. AEs to be assessed from enrollment, throughout study and for the 1 month period (30 days) following last study drug dose; AEs to continue to be assessed for the 3 month (and if necessary 6 month) period following last study drug dose if events associated with study drug persist (to confirm that events have resolved, returned to baseline status, or been adequately explained. Investigator discretion may be used with respect to the method of contact for this AE assessment; clinical events may be followed in writing or by telephone (and documented), an in-person visit will not be required). Any patient who develops pulmonary fibrosis will be followed at approximately 3 month intervals for up to 2 years to assess the course of the disease and evaluate potential reversibility of this finding.
- 5. Vital Signs: To include temperature, pulse, respiratory rate, blood pressure, and pulse oximetry.
- 6. Physical Examination: Complete at screening including height, weight, general appearance, skin, ears, eyes, nose, throat, neck/thyroid, chest/breasts, lungs, heart, abdomen, musculoskeletal system, pulse, lymph nodes, neurologic and mental status; directed thereafter, must include weight and pulmonary assessment. Dose adjustments may be made in the event of noted weight change (± 10% [less at the site's discretion or if required by institution procedures]). Pulmonary findings will be evaluated in detail at each visit by the PI (or physician designee); evaluation to include review of pulmonary symptoms including but not limited to: cough, sputum production, hemoptysis, wheezing, dyspnea, dyspnea on exertion, chest pain, and/or chest pain associated with respirations.
- 7. Hematology Panel: To include CBC with differential, ANC, and platelet count. Evaluation frequency should be increased in the event of hematologic toxicity.
- 8. Serum Chemistry Panel: To include Na, K, Cl, bicarbonate or carbon dioxide, BUN, creatinine, glucose, bilirubin [total and direct], AST, ALT, alkaline phosphatase, Ca, Mg, phosphorous, albumin, total protein, uric acid, amylase, lipase, and CK (in the event of abnormalities while on study, please perform isoenzyme analysis). Evaluation frequency should be increased in the event of significant serum chemistry abnormalities. Clinically significant electrolyte abnormalities should be corrected prior to dosing.
- 9. Coagulation Panel: To include PTT (or aPTT), PT and/or INR
- 10. Urinalysis: Multipanel chemical test strips are acceptable and should include assessment of: specific gravity, pH, protein, glucose, ketones, leukocyte esterase, nitrite, bilirubin, urobilinogen, and occult blood; include microscopic sediment evaluation if clinically indicated if gross findings are abnormal, including WBC/high power field [hpf] and RBC/hpf.
- 11. ADA to AVID100 (Central Lab): To assess immunogenicity; whole blood (~5 mL at each timepoint) will be collected for serum acquisition. In the event that a collected serum sample is inadequate or insufficient for ADA analysis, the analysis of ADA can be done using a PK serum sample from the same time point, if available. Residual sample material may be used for biomarker assessments. See Laboratory Manual (or other similar document) for details regarding collection, handling, and shipping.
- 12. Pregnancy Testing: β-hCG in WOCBP; serum at Screening, urine or serum thereafter; negative test must be confirmed within 2 working days prior to first dose of study drug
- 13. ECG (12-Lead): To include measurement of PR interval, QRS duration, QT interval, and QTc interval [msec], as well as heart rate [BPM]; to be performed after patient has been supine for ≥ 10 minutes; repeat subsequent time points in triplicate separated by 5 minutes for 4 cycles (Day 1 at SOI and EOI) in patients with a QTc that is either: a) > 500 msec; b), increased by 60 msec over

